#### 9.4.2 Joint Evaluation

Anatomical joints are evaluated for swelling and tenderness at every study visit. The 34 anatomical joints in [Table 6](#) are assessed in this study for both the left and right side of the body.

**Table 6. Anatomical Joints Assessed for Calculation of Tender and Swollen Joint Counts (TJC68 and SJC66)**

Temporomandibular	Sternoclavicular	Acromio-clavicular	Shoulder
Elbow	Wrist	Metacarpophalangeal I	Metacarpophalangeal II
Metacarpophalangeal III	Metacarpophalangeal IV	Metacarpophalangeal V	Thumb Interphalangeal
Proximal Interphalangeal II	Proximal Interphalangeal III	Proximal Interphalangeal IV	Proximal Interphalangeal V
Distal Interphalangeal II	Distal Interphalangeal III	Distal Interphalangeal IV	Distal Interphalangeal V
Hip a	Knee	Ankle	Tarsus
Metatarsophalangeal I	Metatarsophalangeal II	Metatarsophalangeal III	Metatarsophalangeal IV
Metatarsophalangeal V	Great Toe/Hallux	Interphalangeal II	Interphalangeal III
Interphalangeal IV	Interphalangeal V		

a. Hip joints are not assessed for swelling.

At each study visit, a joint evaluator assessed whether a particular joint was "tender or painful" where presence of tenderness was scored as "1" and the absence of tenderness was scored as "0," provided the joint was not replaced ("9") or could not be assessed ("NA") due to other reasons (e.g., post-corticosteroid joint injection). The total tender joint count (TJC68), which is based on 68 joints, will be derived as the sum of all "1s" and proportional extrapolation will be used to impute joint counts for the joints that are replaced or not assessed. A similar method will be followed for the derivation of total swollen joint count (SJC66), which is based on 66 joints as the hip joints are excluded. Thus, the range for TJC68 will be 0 to 68 and 0 to 66 for SJC66.

### **9.4.3 Patient's Global Assessment of Disease Activity Visual Analog Scale (VAS)**

The subject will assess his/her disease activity for the past 24 hours using a Patient's Global Assessment of Disease VAS. The range is 0 to 100 mm with no activity being indicated by 0 and severe activity by 100.

#### **9.4.4 Physician's Global Assessment of Disease Activity Visual Analog Scale (VAS)**

The physician will assess Patient's disease activity at the time of visit using a Physician's Global Assessment of Disease VAS. The range is 0 to 100 mm with no activity being indicated by 0 and severe activity by 100.

#### **9.4.5 Patient's Global Assessment of Pain**

The subject will assess his/her pain in the previous week using a Patient's Global Assessment Pain VAS. The range is 0 to 100 mm with no pain being indicated by 0 and severe pain by 100.

#### **9.4.6 Disease Activity Score (DAS28)**

DAS28 (CRP) and DAS28 (ESR) are composite indices to assess disease activity in RA patients using hsCRP or ESR measurement respectively. The DAS provides a score between 0 and 10, indicating how active the rheumatoid arthritis is at the time of measurement.

DAS28 (CRP) and DAS28 (ESR) can be calculated based on Tender Joint Count, Swollen Joint Count, Patient's Global Assessment of Disease Activity (PtGA) (in mm), and hsCRP (in mg/L) or ESR (mm/hr).

$$\text{DAS28 (CRP)} = 0.56 \times \sqrt{(\text{TJC28}^*)} + 0.28 \times \sqrt{(\text{SJC28}^{**})} + 0.36 \times \ln(\text{hsCRP}^{\&} + 1) + 0.014 \times \text{PtGA}^{\gg} + 0.96$$

$$\text{DAS28 (ESR)} = 0.56 \times \sqrt{(\text{TJC28}^*)} + 0.28 \times \sqrt{(\text{SJC28}^{**})} + 0.70 \times \ln(\text{ESR}^{\#}) + 0.014 \times \text{PtGA}^{\gg}$$

\* TJC28 refers to the Subject's total Tender Joint Count out of the provided 28 evaluated joints.

\*\* SJC28 refers to the Subject's total Swollen Joint Count out of the provided 28 evaluated joints.

& hsCRP refers to the high-sensitivity c-reactive protein lab value. hsCRP unit in the DAS28 (CRP) equation is expressed as mg/L.

# ESR refers to the Erythrocyte sedimentation rate. ESR unit in the DAS28 (ESR) equation is expressed as mm/hr.

» PtGA refers to the Patient's Global Assessment of Disease Activity.

where  $\sqrt{\quad}$  is square root and  $\ln$  is natural log.

**Table 7. Anatomical Joints for DAS28 (CRP) Calculation**

Shoulder	Elbow	Wrist	Thumb Interphalangeal
Metacarpophalangeal I	Metacarpophalangeal II	Metacarpophalangeal III	Metacarpophalangeal IV
Metacarpophalangeal V	Proximal Interphalangeal II	Proximal Interphalangeal III	Proximal Interphalangeal IV
Proximal Interphalangeal V	Knee		

To calculate observed DAS28 scores, the observed component value will be calculated first. Then the components will be included in the calculation per the DAS formula selected. If any observed component is missing in a window, then the observed DAS28 score will be missing.

#### **9.4.7 Simplified Disease Activity Index (SDAI)**

SDAI is a composite continuous index to assess disease activity based on TJC28, SJC28, Patient's Global Assessment of Disease Activity (PtGA) (in cm, 0 – 10), Physician's Global Assessment of Disease Activity (PhGA) (in cm, 0 – 10) and hsCRP (mg/dL). It can be derived as follows:

$$\text{SDAI} = \text{TJC28} + \text{SJC28} + \text{PtGA (cm)} + \text{PhGA (cm)} + \text{hsCRP (mg/dL)}.$$

To calculate observed SDAI scores, the observed component value will be calculated first. Then the components will be included in the calculation per the SDAI formula selected. If any observed component is missing in a window, then the observed SDAI score will be missing.

#### **9.4.8 Clinical Disease Activity Index (CDAI)**

CDAI is a composite continuous index to assess disease activity without using hsCRP measurement. It can be calculated based on TJC28, SJC28, Patient's Global Assessment of Disease Activity (PtGA) (in cm, 0 – 10) and Physician's Global Assessment of Disease Activity (PhGA) (in cm, 0 – 10). It can be derived as follows:

$CDAI = TJC28 + SJC28 + PtGA (cm) + PhGA (cm).$

To calculate observed CDAI scores, the observed component value will be calculated first. Then the components will be included in the calculation per the CDAI formula selected. If any observed component is missing in a window, then the observed CDAI score will be missing.

#### 9.4.9 Clinical Remission (CR) and Low Disease Activity (LDA)

Clinical remission (CR) and low disease activity (LDA) based on DAS28 (CRP), DAS28(ESR), SDAI and CDAI are defined as follows:

	DAS28 (CRP) and DAS28 (ESR)	SDAI	CDAI
LDA	$\leq 3.2$	$\leq 11.0$	$\leq 10$
CR	$< 2.6$	$\leq 3.3$	$\leq 2.8$

#### 9.4.10 ACR/EULAR Boolean Remission

ACR/EULAR Boolean remission is defined based on the following four criteria:

- Tender joint count  $\leq 1$  (based on 28 joints)
- Swollen joint count  $\leq 1$  (based on 28 joints)
- CRP  $\leq 1$  mg/dL
- Patient global assessment of disease activity  $\leq 10$  (mm)

All four criteria must be satisfied at a visit for a subject to be classified as achieving ACR/EULAR Boolean remission.

#### 9.4.11 Disability Index of Health Assessment Questionnaire (HAQ-DI)

HAQ-DI is a self-reported patient outcome measurement. It is calculated as the mean of the scores from 8 following categories with a range 0 – 3: Dressing and Grooming,

Rising, Eating, Walking, Hygiene, Reach, Grip, and Activities. The higher the score, the more likely to associate with morbidity and mortality for the RA patient.

The maximum score for all the questions in each category is considered as the score for the category. The Standard disability index (HAQ-DI) takes into account the subject's use of aids or devices or assistance in the scoring algorithm for a disability category. For each of the eight disability categories there is an AIDS OR DEVICES companion variable(s) that is used to record the type of assistance, if any, a subject uses for his/her usual activities. If aids or devices and/or assistance from another person are checked for a disability category, the score for this category is set to 2 (much difficulty), if the original score is 0 (no difficulty) or 1 (some difficulty). The HAQ-DI is then calculated by summing the adjusted categories scores and dividing by the number of categories answered. The HAQ-DI cannot be calculated if the patient does not have scores for at least 6 categories.

#### **9.4.12 EuroQoL-5D (EQ-5D-5L)**

EQ-5D is a standardized measure of health status developed by the EuroQol Group in order to provide a simple, generic measure of health for clinical and economic appraisal. The EQ-5D consists of 2 pages. The first page measures 5 dimensions of the health status (mobility, self-care, usual activities, pain/discomfort, and anxiety/depression) with 5 levels per dimension (no problems, slight problems, moderate problems, severe problems, and extreme problems corresponding to Level 1 to Level 5 respectively). The second page is an EQ Visual Analogue Scale (EQ VAS). EQ-5D health states, defined by the EQ-5D-5L descriptive system on the first page, may be converted into a single index value. The change from baseline of the index value and EQ VAS will be analyzed and reported. UK scoring algorithm will be used.

#### **9.4.13 Insomnia Severity Index (ISI)**

ISI is a 7 item questionnaire that assess, (1) difficulty with sleep onset, (2) difficulty with sleep maintenance (3) problem with early awakening, (4) satisfaction with sleep pattern, (5) interference with daily functioning as a result of sleep problems, (6) noticeability of

sleep problem to others, and (7) degree of distress caused by sleep problem. The severity of insomnia items are rated on a likert type of scale, (0) "None," 1- "Mild," 2- "Moderate," 3- "Severe" and 4- "Very Severe." Other items on satisfaction, noticeability on impairment, worry/distress about sleep and interference are similarly rated on 5-point likert type scale form. The scoring algorithm is in the protocol.

#### **9.4.14 Form SF-36v2**

The 36-Item Short Form, Version 2 (SF-36v2) Questionnaire with 4 week recall will be completed by the subject at Baseline, Weeks 4, 8 and at study completion (Week 12 or at PD). The SF-36v2 health survey consists of 36 general health questions and this study is using the form for 4 weeks recall period (standard form). It has 2 components: physical and mental. For each component, a transformed summary score is calculated using 8 sub domains: physical functioning, role-physical, bodily pain, general health, vitality, social functioning, role-emotional, and mental health.

The coding and scoring for the SF-36 will use the software provided by QualityMetrics.

## **10.0 Safety Analysis**

### **10.1 General Considerations**

Safety analyses will be carried out using the Safety Analysis Set. There are two sets of planned safety analysis: safety analysis by Week 12, and long-term safety analysis.

#### **Safety Analysis by Week 12**

Standard safety analysis by the "as treated" treatment groups of Upadacitinib 15 mg QD, Upadacitinib 30 mg QD, and combined placebo groups will be performed on safety data up to Week 12. No protocol-defined treatment switching will occur prior to these time points.

The standard safety analyses will include reporting of adverse events (AEs), laboratory, and vital signs measurements. Frequency tables of subjects with treatment-emergent

adverse events (TEAEs) by system organ class (SOC) and by preferred term (PT) as in the Medical Dictionary for Regulatory Activities (MedDRA) dictionary will be provided by treatment group. Mean changes from baseline in all continuous laboratory parameters and vital signs variables at each visit will be summarized by "as treated" treatment group. Frequency tables of subjects meeting criteria for potentially clinically significant vital sign values and for potentially clinically significant laboratory values will be provided by treatment group. Missing safety data will not be imputed.

### **Long-Term Safety Analysis**

Long-term safety analyses that account for protocol-defined treatment switching include reporting of AE rate adjusted by cumulative exposure, mean change from baseline in laboratory parameters and vital sign variables, and rate of potentially clinically significant laboratory and vital signs values. The treatment-emergent adverse event (TEAE) rate per 100 patient-years of exposure will be presented by actual treatment received at the time of AE (as described in Section 10.2.2). Listing of subjects with TEAEs by SOC and PT will be provided. Mean changes from baseline in all continuous laboratory parameters and vital signs variables at each visit will be summarized by "as treated" treatment group sequences defined as follows (as described in Section 10.3.3 and Section 10.4.3). Frequency tables and listings of subjects meeting criteria for potentially clinically significant vital sign values and for potentially clinically significant laboratory values will be provided by actual treatment received at the time of event. Missing safety data will not be imputed.

"As treated" treatment group sequences:

1. Placebo → Upadacitinib 15 mg QD
2. Placebo → Upadacitinib 30 mg QD
3. Upadacitinib 15 mg QD
4. Upadacitinib 30 mg QD.

Starting with Amendment 4, all subjects will receive open-label upadacitinib 15 mg QD, including those currently on upadacitinib 30 mg QD. For subjects who previously received upadacitinib 30 mg QD, adverse events and exposure to upadacitinib 30 mg QD will be censored at the time of dose switch; subsequent adverse events and exposure starting the day of first dose of upadacitinib 15 mg QD will be summarized under a separate group, as defined in Section 9.1. Assessment of potentially clinically significant laboratory and vital sign values will be based on the same treatment exposure groups as for adverse events, as described above. For summary of mean change from baseline in laboratory values and vital signs, exposure sequences 2 and 4 (i.e., subjects who switched from upadacitinib 30 mg QD to 15 mg QD) will be censored at the time of dose switch. Mean change from baseline for laboratory values and vital signs collected after dose switch will be summarized separately by visits post switch.

## **10.2 Analysis of Adverse Events**

A treatment-emergent Adverse Event (TEAE) is defined as an adverse event with an onset date that is after the first dose of study drug, and no more than 30 days of the drug after the last dose of study drug.

Events where the onset date is the same as the study drug start date are assumed to be treatment-emergent, unless the study drug start time and the adverse event start time are collected and the adverse event start time is prior to the study drug start time. If an incomplete onset date was collected for an adverse event, the event will be assumed to be treatment-emergent unless there is other evidence that confirms that the event was not treatment-emergent (e.g., the event end date was prior to the study drug start date).

Adverse event data will be presented by SOCs and PTs using MedDRA Version 19.1 or most up to date version. All adverse event tables will be sorted in alphabetical order by SOC and PT and descending percentages for each treatment group.

## **10.2.1 Analysis of Adverse Events Prior to Protocol-Defined Treatment Switching**

### **10.2.1.1 Adverse Events Overview**

The number and percentage of subjects experiencing TEAEs will be summarized by "as treated" treatment group and overall for the following AE categories.

- All TEAEs
- Treatment-emergent serious adverse events (SAEs)
- Treatment-emergent severe adverse events
- TEAEs reasonably possibly related to study drug
- TEAEs of special interest
- TEAEs leading to discontinuation of study drug
- TEAE leading to death

In the AE overview summary, any event with an unknown severity will be considered as severe and any AE with an unknown relationship will be considered as having "reasonable possibility" of being related to study drug.

Additional AEs may be considered for tabulation/summary based on recommendations from Clinical and Safety as deemed appropriate.

For TEAEs of special interest, the point estimate and 95% CI (using normal approximation) will be provided for the treatment difference in AE percentage between each Upadacitinib dose group and the combined placebo group.

As a sensitivity analysis, the AE overview summary will be repeated by randomized treatment groups (Upadacitinib 15 mg QD, Upadacitinib 30 mg QD and the combined placebo groups). In this summary, all AEs with an onset date after the first dose of study drug will be included, regardless of whether the AE occurred more than 30 days after the last dose of study drug.

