#### **4.2 Overall Study Design and Plan**

This is a Phase 3, multicenter study that includes two periods. Period 1 is the 24-week randomized, double-blind, parallel-group, placebo-controlled period designed to compare the safety and efficacy of Upadacitinib 30 mg QD and 15 mg QD versus placebo for the treatment of signs and symptoms of subjects with moderately to severely active RA who have an inadequate response to or intolerance to bDMARD therapy and are currently on a stable dose of csDMARDs. Period 2 is a blinded long-term extension to evaluate the

long-term safety, tolerability, and efficacy of Upadacitinib 30 mg QD and 15 mg QD in subjects with RA who have completed Period 1. Starting with Amendment 4, all subjects will receive open-label upadacitinib 15 mg QD, including those currently on upadacitinib 30 mg QD.

The study is designed to enroll approximately 450 subjects at approximately 350 study centers worldwide to meet scientific and regulatory objectives without enrolling an undue number of subjects in alignment with ethical considerations. Therefore, if the target number of subjects has been enrolled, there is a possibility that additional subjects in screening may not be enrolled.

The study duration includes a 35-day screening period; a 24-week randomized, double-blind, parallel-group, placebo controlled treatment period (Period 1); a 236-week blinded extension period (Period 2); and a 30-day follow-up (call or site visit).

Subjects who meet eligibility criteria will be randomized in a 2:2:1:1 ratio to one of four treatment groups:

- Group 1: Upadacitinib 30 mg QD, N = 150 (Day 1 to Week 12) → Upadacitinib 30 mg QD (Week 12 and thereafter)
- Group 2: Upadacitinib 15 mg QD, N = 150 (Day 1 to Week 12) → Upadacitinib 15 mg QD (Week 12 and thereafter)
- Group 3: Placebo, N = 75 (Day 1 to Week 12) → Upadacitinib 30 mg QD (Week 12 and thereafter)
- Group 4: Placebo, N = 75 (Day 1 to Week 12) → Upadacitinib 15 mg QD (Week 12 and thereafter)

Randomization is stratified by number of prior bDMARD (stratum 1: failed 1 or 2 biologics with the same mechanism of action; stratum 2: failed  $\geq 3$  biologics with the same mechanism of action and/or multiple mechanisms of action) and geographic region.

Subjects must have been receiving csDMARD therapy  $\geq 3$  months and have been on a stable dose of csDMARD(s) for  $\geq 4$  weeks prior to the first dose of study drug and must

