## **4.3 Sample Size**

The planned total sample size of 450 can provide approximately 90% power to detect a 20% difference in ACR20 rates at Week 12 (assuming a placebo ACR20 response rate of 27%), at two-sided  $\alpha = 0.025$  and accounting for 10% dropout rate. This sample size also provides approximately 90% power for a 17% difference in DAS28 (CRP) LDA response rate at Week 12 (assuming a placebo DAS28 LDA response rate of 12%), at two-sided  $\alpha = 0.025$  and accounting for 10% dropout rate. It can also provide at least 90% power

for most key secondary endpoints, at two-sided significance level of 0.025 and accounting for a 10% dropout rate.

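### Week 12 differences in adverse events of special interest get a normal-approximation 95% CI with no sparse-event fallback; for single rare categories it collapses to [0, 0] at 0 versus 0 and tends to understate excess risk.

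*SAP*

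**What the plan says.** SAP 10.2.1.1 (Adverse Events Overview) covers events before the protocol-defined switch at Week 12. For treatment-emergent AESIs, "the point estimate and 95% CI (using normal approximation) will be provided for the treatment difference in AE percentage". The contrast is each dose against the two placebo arms pooled. The section names no exact or score method, no continuity correction and no minimum event count.

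The group sizes come from SAP 4.2. Subjects are "randomized in a 2:2:1:1 ratio". Each dose arm is planned as in "Upadacitinib 30 mg QD, N = 150 (Day 1 to Week 12", and each of the two placebo arms as in "Placebo, N = 75 (Day 1 to Week 12". Every comparison is therefore 150 against 75 + 75 = 150.

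The AESI categories are in SAP 10.2.1.6 and Table 8. They include lymphoma, active tuberculosis, adjudicated gastrointestinal perforation, MACE and venous thromboembolism, and also commoner categories such as anemia, CPK elevation and herpes zoster. That section specifies no interval.

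Three other places matter:
- SAP 10.2.2.1 uses the same normal approximation for long-term AESI rate differences per 100 patient-years against combined placebo.
- SAP 10.3.2.3 uses Fisher's exact test for potentially clinically significant laboratory values.
- SAP 11.1 states that Period 1 reporting was completed under version 2.0 and that version 3.0 governs only later long-term reporting.

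**The concern.** The usual normal-approximation (Wald) interval takes its width from the observed proportions. With no events in an arm, that arm contributes no variance. With no events in either arm, the interval has zero width, so the table would show 0.0 to 0.0 when the data say least.

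A safety interval is read mainly for its upper end: how large an excess risk do the data still allow? If events are few and occur only on drug, the Wald upper limit is too low. The error then runs in the direction that makes the drug look safer.

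**Working it through.** **The plan's own figure.** The documents give no coverage figure for these intervals. The nearest stated figure on the same group sizes is the power in SAP 4.3: "The planned total sample size of 450 can provide approximately 90% power to detect a 20% difference in ACR20 rates at Week 12" (27% versus 47%), and "approximately 90% power for a 17% difference in DAS28 (CRP) LDA response rate at Week 12" (12% versus 29%). With 10% dropout, n = 150 × 0.9 = 135 per group. At two-sided alpha 0.025, z = 2.2414.

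Power = Φ[(Δ − z·√(2p̄q̄/n)) / √((p₁q₁ + p₂q₂)/n)].
- ACR20: (0.20 − 2.2414 × 0.0588)/0.0575 = 1.19, power 88.3% (89.2% with unpooled variance).
- LDA: (0.17 − 2.2414 × 0.0491)/0.0480 = 1.25, power 89.4% (90.3% unpooled).

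Both agree with the stated approximately 90%, which confirms 150 versus 150 as the comparison.

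**The interval for given counts.** Wald: d ± 1.96·√(p̂₁q̂₁/150 + p̂₂q̂₂/150). Newcombe combines the two Wilson intervals. At 0 versus 0 its limits are ±z²/(n + z²) = ±3.84/153.84 = ±2.5 points. At 1 versus 0, the Wald upper limit is 0.00667 + 1.96 × 0.00664 = 1.97 points.

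| Events, drug vs placebo | Wald (points) | Newcombe | Miettinen-Nurminen |
|---|---|---|---|
| 0 vs 0 | 0.00 to 0.00 | -2.50 to 2.50 | -2.50 to 2.50 |
| 1 vs 0 | -0.64 to 1.97 | -1.89 to 3.68 | -1.84 to 3.68 |
| 3 vs 0 | -0.24 to 4.24 | -0.82 to 5.71 | -0.53 to 5.72 |

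**Coverage.** This is by full enumeration of two independent binomials with n = 150 each. The true rates are assumptions.

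| True rates, drug vs placebo | Wald | Newcombe |
|---|---|---|
| 0.5% vs 0% | 52.8% | not tabulated |
| 1% vs 0% | 77.8% | 99.9% |
| 1.96% vs 0% | 94.6% | not tabulated |
| 2% vs 0% | 80.0% | 99.7% |
| 3% vs 0% | 93.6% | 98.4% |
| 1% vs 0.5% | 88.4% | 99.6% |
| 2% vs 1% | 93.3% | 98.0% |
| 0.5% vs 0.5% | 99.3% | 99.9% |
| 10% vs 5% (as for a pooled line) | 95.0% | not tabulated |

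**Where the misses come from.**
- 0.5% vs 0%: the chance of 0 versus 0 is 0.995^150 = 47.1%, which is almost the whole shortfall.
- 1% vs 0%: 0.99^150 = 22.1%, out of 22.2% missed. The interval lies below the true excess in all but about 0.1% of trials.
- 1% vs 0.5%: 0.2215 × 0.4715 = 10.4%, out of 11.6% missed.
- 2% vs 0%: the 1-versus-0 limit of 1.97 just fails to reach 2.0, so P(0) + P(1) = 4.8% + 14.8% = 19.6% is missed. At 1.96% the same limit reaches the truth and coverage returns to 94.6%.

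**Sensitivity.** A pooled variance gives the same coverage at 1% and 2% versus 0% and the same collapse at 0 versus 0. A continuity correction gives ±0.67 points at 0 versus 0 and still covers 77.8% at 1% versus 0%. With 135 per group, coverage is 49%, 74% and 93% at 0.5%, 1% and 2% versus 0%.

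**Long-term rates (SAP 10.2.2.1).** Placebo exposure is at most about 150 × 84/365.25 = 34.5 patient-years. With no placebo events the normal approximation gives the placebo rate no uncertainty. Yet zero events in 34.5 patient-years is compatible with up to −ln(0.05)/34.5 = 8.7 per 100 patient-years (one-sided 95%).

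**The case against.** **The Week 12 analysis is finished.** SAP 11.1 says so, and SAP Appendix B dates it to 2017. This stands: an edit to 10.2.1.1 creates no new planned output. The section does remain in the current SAP, where 11.1 lists it among those clarified, and 10.2.2.1 is still live.

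**The interval may be meant for one pooled AESI line.** The sentence sits in the overview, where AESIs are a single item in the list, and 10.2.1.6 asks for no interval by category. This also stands as an ambiguity. On the pooled reading coverage is near nominal and the Week 12 concern largely disappears. Nothing in the text limits the interval to a pooled line, though.

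**The low coverage figures depend on the chosen rates.** Correct. A reader might infer a steady coverage of about 80% for rare events. The documents do not support that: they give no AESI rates for this trial, and the 2% versus 0% figure reverses with a 0.04-point shift in the assumed rate. Nor do they show that most categories will have only a handful of events. Protocol 3.0 gives hints both ways from Phase 2. Two malignancy subjects are reported on upadacitinib, which is about 0.4% if some 470 received it. Herpes zoster was 1.3% on drug and 1.9% on placebo, where Wald coverage is 93.9%.

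**Little hangs on the interval.** No decision rule uses it, counts and percentages appear beside it, and Newcombe is itself conservative. This limits the severity. It does not rescue a zero-width interval, which follows from the formula whatever the true rates.

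**Conclusion.** The concern holds in a limited form. If the Week 12 interval is applied to individual Table 8 categories, it is uninformative at 0 versus 0 and its upper limit is too low when the few events fall only on drug. Under the assumed rates, coverage runs from 53% (0.5% versus 0%) through 78% (1% versus 0%) to between 80% and 95% around 2% versus 0%. It is 93% at 2% versus 1%, and above nominal when both rates are equal at 0.5%. At the lowest rates most of the shortfall is the zero-width 0-versus-0 table, so the two symptoms are largely one defect.

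These figures assume 150 per group, independent binomial counts, the standard Wald form, and true rates that are not in the documents. It would go too far to conclude that the reported Week 12 safety results are wrong or that every AESI row is affected: the documents show neither the counts nor which lines received an interval. The point that still bears on planned output is the long-term rate difference in 10.2.2.1.

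**What to change.** - **SAP 10.2.1.1:** state whether the interval is by category, and for each AESI category replace the normal approximation with a Miettinen-Nurminen or Newcombe interval for the risk difference. Because Period 1 has been reported, apply this as a supplementary re-run of the Week 12 AESI table, or as a footnote where counts are sparse.
- **SAP 10.2.2.1:** before long-term reporting, replace the normal approximation with an exact or score-based Poisson interval for the difference in rates. An interval for proportions does not fit event rates. The numerator counts repeat events within a subject, so note the independence assumption.

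The Week 12 interval is one option in PROC FREQ plus the effort of the re-run; the rate interval needs a little more programming. The intervals become wider and somewhat conservative. No new data are needed, and efficacy and alpha are untouched.
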